We treat an average of 16,000 outpatients a year; over 50% of these patients carry a diagnosis of advanced lung disease, including COPD, IPF, pulmonary hypertension, and bronchiectasis. We are a major referral center for lung volume reduction surgery.

All physicians, nurses and ancillary staff members will be instructed in the details of this study.

9) Prior Approvals

Not applicable.

10) Study Design

a) Recruitment Methods

Thirty patients hospitalized for acute exacerbation of COPD \leq the last 12 weeks will be enrolled into the study. Subjects will be recruited from the Temple Lung Center clinical practices in Philadelphia and Oaks, PA.

Potential subjects will be recruited during scheduled office visits to the Temple Lung Center offices in Philadelphia and in Oaks, PA. Many of these patients will be those who have been referred to Temple. We will also contact pulmonology practices in the tri-state area through direct mailings and our monthly research fax blast. The Temple Lung Center also maintains an IRB-approved registry of patients who have agreed to be contacted to discuss participation in clinical research trials.

Describe materials that will be used to recruit subjects. Include copies of these documents with the application. – Not applicable

Subjects will receive compensation in the form of a \$25 gift card for each completed visit during their participation in this study.

b) Inclusion and Exclusion Criteria

Consecutive patients \geq 40 years of age or older who are admitted to the hospital for an acute exacerbation of COPD within the past 12 weeks. Patients will have COPD as the primary diagnosis and have smoked > 10 pack years. Patients should be receiving supplemental oxygen as part of their usual clinical care.

Patients must be willing to give informed consent and be willing to participate in measurement of ABGs, brief history and physical examination and answer questionnaires regarding daily use of HNHF-O2 therapy. Women who are pregnant are excluded from this research. Women of childbearing potential will have a urine pregnancy test to ensure that they are not pregnant.

The main exclusion criteria are upper airway or nasal problems that prohibit the use of high flow oxygen and patients with any of the following will be excluded:

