current use (\leq 4 weeks of study entry) of any PAP-therapy (e.g., CPAP or NPPV); sleep apnea as follows: STOPBang scores \geq 5 or STOPBang score \geq 2 plus BMI $>$ 35 kg/m²; or Berlin questionnaire scores suggesting high likelihood of sleep apnea with increased risk of sleep-related accident (e.g., occupation as a commercial driver or pilot); or excessive daytime sleepiness (i.e., either of High (>15) score on the Epworth Sleepiness Scale or “fall asleep” accident or “near miss” accident in prior 12 months).

c) Local Number of Subjects

Thirty subjects will be accrued locally for this study.

We expect few screen failures.

d) Study-Wide Number of Subjects

If this is a multicenter study, indicate the total number of subjects to be accrued across all sites. – Not applicable.

e) Study Timelines

- Subjects will be followed for 90 days with regular telephone follow-up and clinic visits throughout.
- Subjects will be enrolled over a period of 12 months.
- The investigators will complete the data analysis approximately 18 months after the first subject is enrolled.

f) Study Endpoints

The primary endpoints of this study are the feasibility of oxygen therapy by HNHF-O2 at home over a 90-day period in terms of tolerance and hours of use. Descriptive statistics will be used to characterize the patient population in terms of demographic factors and severity of airflow obstruction. Changes in PaO₂, PaCO₂ and pH across the days will be done by analysis of variance. The effect of baseline PaCO₂ on change in PaCO₂ with HNHF-O2 therapy will be analyzed as an independent effect on change in PaCO₂ levels with HNHF-O2. Changes in respiratory rate, heart rate, blood pressure accessory muscle use will also be assessed by analysis of variance. Patient tolerance and side effects will also be measured across days of use per patient and across days in all patients as group trends. Hours of use per device log and per patient diary will be independently analyzed and compared to one another. The impact on change in exacerbation frequency and severity will be analyzed. Changes in spirometry, 6MWD, GOLD grade and class and BODE scores prior to and after 90 days of HNHF-O2 will be analyzed.

g) Procedures Involved in the Human Research

[figure not shown]
An overview of the study is provided in the figure below.

Outpatient HNHF-O2 Protocol

Version 3.0

10/06/2017

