Feasibility of using daily home HNHF-O2 during Sleep and/or Daytime in Hypercapnic COPD patients following recent (< 12 wks.) hospitalization for AECOPD for 90 days

¹ > 40 yrs. Age and Hospitalized for AECOPD; able to sign IC and willing to do tests

² vital signs, respiratory patient discomfort, Likert scale for clinical improvement, dyspnea (modified Borg Score, mMRC) ABG 5 minutes after inspiring O₂ to maintain SaO₂ >90%, spirometry, 6 MWT, questionnaires (CAT, SGRQ), set baseline diary for respiratory symptoms

³ Inquire about any problems and assess for adherence, troubleshoot

⁴ vital signs, respiratory patient discomfort, Likert scale for clinical improvement, dyspnea, side effects of HNHF-O₂, and review daily electronic diary of respiratory symptoms

⁵ Same as #2

Patients who have had a recent COPD exacerbation (<12 weeks since discharge) accompanied with respiratory failure who meet the above inclusion criteria will be considered for participation in the study.

Once informed consent has been obtained patients will be given the opportunity to participate in the sleep substudy until the enrollment goal of ten subjects has been achieved. A separate protocol and consent form has been submitted for this study. The following procedures will be performed as part of the main study:

Outpatient HNHF-O2 Protocol

Version 3.0

10/06/2017

Test	Visit 1 Screening	Visit 1a Baseline	Visit 2 Clinic Placed on HNHF-O2	Visit 3 Phone Call Day 1	Visit 4 Phone call Day 3 ± 3	Visit 5 Clinic Day 7 ± 5	Visit 6 Phone call Day 17 ± 3	Visit 7 Clinic Day 28 ± 5	Visit 8 Phone call Day 37 ± 3	Visit 9 Clinic Day 49 ± 5	Visit 10 Phone call Day 58 ± 3	Visit 11 Clinic Day 70 ± 5	Visit 12 Phone call Day 80 ± 3	Visit 13 Clinic Day 90 ± 5
Screen	X													
Informed Consent	X													
History & Physical		X				X		X		X		X		X
Pregnancy test for women of childbearing potential		X												
Arterial blood gas◆		X	X											x
Pre- and Post- Bronchodilator Spirometry		X												X
6 minute walk distance		X												X
mMRC Questionnaire		X ²												
Borg Questionnaire		X ²	X			X		X		X		X		X
Assess Accessory Muscle use		X	X			X		X		X		X		X
Assess subject comfort		X	X			X		X		X		X		X

Outpatient HNHF-O2 Protocol

Version 3.0

10/06/2017

Test	Visit 1	Visit 1a	Visit 2	Visit 3	Visit 4	Visit 5	Visit 6	Visit 7	Visit 8	Visit 9	Visit 10	Visit 11	Visit 12	Visit 13

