	Screening	Baseline	Clinic Placed on HNHF- O2	Phone Call Day 1	Phone call Day 3 ± 3	Clinic Day 7 ± 5	Phone call Day 17 ± 3	Clinic Day 28 ± 5	Phone call Day 37 ± 3	Clinic Day 49 ± 5	Phone call Day 58 ± 3	Clinic Day 70 ± 5	Phone call Day 80 ± 3	Clinic Day 90 ± 5
Epworth Sleepiness Scale	X													
Berlin Sleep Questionnaire	X													
STOP-Bang Questionnaire	X													
St. George's Respiratory Questionnaire		X												X
GOLD Category		x												
BODE Index		X												X
Daily Diary	X	X	X			X		X		X		X		X
COPD Activity Test		X												X
Review current medications	X	X	X	X	X	X	X	X	X	X	X	X	X	X
Phone call				X	X		X		X		X		X	
Sleep substudy participants														
Insomnia Severity index		X												
Home sleep study		X ¹				X						X		
Epworth Sleepiness		X ²				X ²						X ²		

Outpatient HNHF-O2 Protocol

Version 3.0

10/06/2017

Scale														
-------	--	--	--	--	--	--	--	--	--	--	--	--	--	--

¹ For those subjects enrolled in the sleep substudy the acquaintance and baseline sleep studies must be completed before beginning HNHF-O2

² Questionnaires are done at baseline visit and repeated at home prior to the baseline, day 7, and day 70 sleep studies.

◆ For ABGs, the test will be done on room air after the participant has been off the Airvo device for 20 minutes. If the participant starts to desaturate, then it can be done on 2L of oxygen.

Outpatient HNHF-O2 Protocol

Version 3.0

10/06/2017

There will be collection of demographic data including age, gender, race, current medications, and comorbid conditions. A patient history of duration of the nature and course of prehospital symptoms, past medical history of smoking, and past use of respiratory medications and nonpharmacological therapy for COPD will be elicited. Historical collection of available clinical data including exacerbation history, reports of chest imaging as well as pulmonary function and/or exercise or cardiac data will be collected.

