At baseline, patients will have measurement of vital signs (heart rate, respiratory rate and blood pressure), dyspnea (modified Borg score, mMRC) arterial blood gas after 5 minutes of inspiring supplemental oxygen to keep $\text{SaO}_2 > 90\%$, and use of accessory muscles of ventilation. Patients will have spirometry performed pre-and post-bronchodilator administration. Patients will have assessment of their current respiratory health by completing CAT, mMRC and SGRQ questionnaires. A detailed history of their exacerbation frequency and severity will be obtained. Patients will perform a 6-minute walk test. Patients GOLD grade and group will be classified and patients BODE scores will be calculated.

Patients will be queried regarding the presence and magnitude of complaints of cough and sputum production by using a daily electronic diary for a 2-week period of run in. After the 2-week run-in period the patient will be scheduled to return to initiate HFNC with oxygen therapy.

Electronic daily diary of respiratory symptoms.

- ❖ Breathlessness (Modified Borg Scale)
- ❖ Sputum Quantity, Color, and Consistency
- ❖ Peak Flow Measurements
- ❖ Presence of Temperature Over 100°F
- ❖ Presence of Any Cough, Wheeze, Sore Throat or Nasal Congestion

Outpatient HNHF-O2 Protocol

Version 3.0

10/06/2017

Patients will be seen in clinic and instructed in the use of HNHF-O2 and its proposed benefits. The necessity of compliance and adherence to the treatment plan will be emphasized.

Following the outpatient clinic visit, patients will be set up at home using an established home vendor for respiratory equipment. Patients will continue to report their daily respiratory symptoms via the electronic diary.

Post placement on optimal dose of HNHF-O2 therapy, subjects will be called the next day to determine if there were any problems.

Patients will report to clinic at baseline and then 7 ± 2 , 28 ± 5 , 49 ± 5 , and 70 ± 5 days for the following assessment:

- Measurements of vital signs (heart rate, respiratory rate and blood pressure)
- Respiratory patient-discomfort and dyspnea assessed using an unmarked 100 mm visual analogic scale from “no discomfort” to “maximal imaginable discomfort”
- Likert scale model indicating marked improvement (+2), slight improvement (+1), no change (0), slight deterioration (-1) and marked deterioration (-2)

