- Side effects related to high flow nasal administration: nasal dryness, epistaxis, nasal crusting, eye discomfort, pressure discomfort, increase rhinitis, decreased smell, post nasal drip, hoarseness
- Hours of daily use of HNHF-O2 therapy
- Daily record keeping of daily diary review

At day 90 ± 2 the following will be measured:

- Measurements of vital signs (heart rate, respiratory rate and blood pressure)
- Respiratory patient-discomfort and dyspnea assessed using an unmarked 100 mm visual analogic scale from “no discomfort” to “maximal imaginable discomfort”
- Likert scale model indicating marked improvement (+2), slight improvement (+1), no change (0), slight deterioration (-1) and marked deterioration (-2)
- Side effects related to high flow nasal administration: nasal dryness, epistaxis, nasal crusting, eye discomfort, pressure discomfort, increase rhinitis, decreased smell, post nasal drip, hoarseness
- Hours of daily use of HNHF-O2 therapy
- Daily record keeping of daily diary review
- Arterial blood gas on room air after the participant has been off the Airvo Device for 20 minutes.
- Pre-and post-bronchodilator spirometry

Outpatient HNHF-O2 Protocol

Version 3.0

10/06/2017

- CAT, SGRQ
- 6 Minute walk test
- GOLD grade and group will be classified
- BODE scores will be calculated.

Application of HNHF-O2 therapy. During HNHF-O2, oxygen will be passed through a heated humidifier (myAIRVO 2, Fisher and Paykel Healthcare) and applied continuously through large-bore binasal prongs, with a gas flow rate of 20-35 liters per minute (or as high as tolerated). Temperature will be adjusted based on patient's comfort and range from 34-37 degrees based on prior experience. The fraction of oxygen in the gas flowing in the system will be adjusted to maintain an SpO2 of 90% or more. High-flow oxygen will be applied at the highest tolerated flow up to 35 lpm at home. Meter time and patient's log of hours of daily use will be measured and compared.

Hypercapnic COPD patients are encouraged to use supplemental oxygen therapy on a continuous basis. The use of the humidified nasal high-flow device in this protocol is not expected to change the total number of hours that the patient receives supplemental oxygen; however it will change the manner in which the oxygen is delivered. Patients will be encouraged to use the device for oxygen delivery as many hours per day as possible.

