In order to reduce the risk of contamination and extend the life of the tubing and patient interface it is recommended that the user clean the device at specified intervals. The patient interface should be washed in tap water and reconnected to the heated breathing tube. Thereafter, the device should be run in drying mode. This process takes about 90 minutes to complete and should be performed daily. On a weekly basis the heated breathing tube should be removed along with the patient interface and both washed in warm water with a mild detergent. The outside of the device should be wiped clean with a damp cloth. The inside of the heated breathing tube connection port should be cleaned with a low-lint cloth with mild dishwashing detergent.

The patient has the option to not receive supplemental oxygen during each of these cleaning procedures or to receive supplemental oxygen via a standard nasal cannula.

All supplies necessary for the maintenance of the device will be provided to the subject at no cost to them.

Study procedures:

History and physical exam, vital signs. These are all procedures routinely performed as standard of care.

Lung function testing (spirometry). Pre- and post-bronchodilator testing (spirometry) will be performed according to ATS standards. The bronchodilator

Outpatient HNHF-O2 Protocol

Version 3.0

10/06/2017

medication (albuterol) opens up the airways and will be used in lung function testing. This medication is often used to treat people with COPD. Spirometry will be performed by experienced study personnel.

Arterial blood gases. Arterial blood gases will be obtained from the radial artery in the wrist by experienced personnel. Blood gases will be obtained on room air after the patient has been off the Airvo device for 20 minutes.

6 minute walk test. Subjects will be asked to walk as far as they can for 6 minutes while receiving supplemental oxygen. Testing will be supervised by experienced study personnel with access to emergency medicine such as sublingual nitroglycerin, aspirin and albuterol.

Dyspnea questionnaires, accessory muscle use, and comfort assessments.

The Borg dyspnea questionnaire and mMRC are short questionnaires that can be completed in a minute or two. These questionnaires are included with this submission. Use of accessory muscles requires only subject observation.

Subject comfort assessments are also provided with this submission and can be completed in a minute.

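### The protocol sets conflicting oxygen conditions for the arterial blood gas, so changes from baseline in PaO2, PaCO2 and pH may not compare like with like

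*Combined protocol and SAP*

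**What the plan says.** Section 10(g) describes the blood gas in five places.

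- Study overview, note 2 (baseline): "ABG 5 minutes after inspiring O₂ to maintain SaO₂ >90" percent.
- Baseline measurements: "arterial blood gas after 5 minutes of inspiring supplemental oxygen to keep" SaO2 above 90%.
- Schedule footnote, whose symbol sits on the blood-gas row (marked at Visits 1a, 2 and 13): "For ABGs, the test will be done on room air after the participant has been off the Airvo device for 20 minutes". It continues: "If the participant starts to desaturate, then it can be done on 2L of oxygen". It defines no desaturation level and no time on 2 L before the draw, and it does not require the same condition at paired visits.
- Day 90 measurements: "Arterial blood gas on room air after the participant has been off the Airvo Device for 20 minutes".
- Study procedures, arterial blood gases in general: "Blood gases will be obtained on room air after the patient has been off the Airvo device for 20 minutes".

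The last two do not mention the 2 L option. Section 10(f), repeated in 10(i), gives the analysis: "Changes in PaO₂, PaCO₂ and pH across the days will be done by analysis of variance". Baseline PaCO2 is the only further term named for the gases. Section 10(b) adds: "Patients should be receiving supplemental oxygen as part of their usual clinical care".

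**The concern.** PaO2 depends directly on inspired oxygen, and in hypercapnic patients PaCO2 may too. A before-after change can be read as an effect of 90 days on the device only if both gases were drawn on the same oxygen. Here the baseline gas has two incompatible instructions, and the footnote lets one patient be drawn on room air at one visit and on 2 L at another. Because enrolled patients should already be on oxygen, use of the 2 L option is foreseeable. The analysis has no oxygen term and no rule for mismatched pairs.

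At stake is the gas-exchange result. It is not primary, but Section 1 names long-term stabilisation or improvement of gas exchange as missing evidence. Each of the three arterial punctures should yield a usable comparison.

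**Working it through.** **1. The texts side by side.** There is no figure in the plan to reproduce, so the first step is to see what each reading implies.

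| Reading | Visit 1a | Visit 2 | Visit 13 |
|---|---|---|---|
| A: baseline paragraph, then Day 90 list | titrated oxygen | room air (footnote, general procedure) | room air |
| B: schedule footnote at every draw | room air or 2 L | room air or 2 L | room air or 2 L |

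Reading A mismatches comparisons with Visit 1a. Visit 2 against Visit 13 stays under one rule. Reading B mismatches only patients who change condition between draws.

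**2. Shift per mismatched pair (assumed inputs).** Alveolar gas equation at 760 mmHg with PaCO2 constant:

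change in PaO2 = (a/A ratio) × 713 × change in inspired oxygen fraction.

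Assume that 2 L adds 0.03 to 0.08 to the fraction and that a/A is 0.4 to 0.7. Low end: 0.4 × 713 × 0.03 = 8.6 mmHg. High end: 0.7 × 713 × 0.08 = 39.9 mmHg. The high end does not fit a patient who needs the 2 L option. At PaCO2 50, room-air alveolar PO2 is 0.21 × 713 − 50/0.8 = 87.2, so a/A 0.7 gives PaO2 61. If 2 L is triggered below 55 (assumed), the largest a/A is 55/87.2 = 0.63, and the shift is at most 0.63 × 713 × 0.08 = 36 mmHg.

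**3. Reading A, PaO2.** Two ways to bound the false fall from Visit 1a to Day 90 when nothing truly changes:

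- *Titration stops near target.* Assume that oxygen lifts PaO2 to T = 60 to 65 in anyone below T, that room-air PaO2 is normal with mean μ and SD 8, and that nobody uses 2 L at Day 90. The mean gap is (T − μ)Φ(z) + 8φ(z), with z = (T − μ)/8. This gives 8.7 to 13.2 mmHg for μ = 52, 3.2 to 6.3 for μ = 60, and 0.7 to 1.9 for μ = 68.
- *Everyone gets at least the 2 L gain at baseline.* The mean shift is the per-pair shift × net share mismatched. With 10 of 30 using 2 L at Day 90 (net 20): 8.6 × 20/30 = 5.7 up to 39.9 × 20/30 = 26.6 mmHg. The upper part needs oxygen well above the titration target.

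As an illustration, a 5 mmHg false fall with an assumed SD of change of 10 and n = 30 would reach two-sided 5% significance about 75% of the time.

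**4. Reading A, PaCO2.** If oxygen raises PaCO2 by 0 to 5 mmHg (assumed), removing it in a net 20 of 30 gives a false fall of 0 to 5 × 20/30 = 3.3 mmHg, in the direction of benefit.

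**5. Reading B, one patient.** PaCO2 50, a/A falling from 0.65 to 0.55. Room-air PaO2 goes from 0.65 × 87.2 = 56.7 to 0.55 × 87.2 = 48.0, a true fall of 8.7. Drawn on 2 L at Day 90, the value is 0.55 × (87.2 + 21.4 to 57.0) = 59.7 to 79.3, a recorded rise of 3.0 to 22.6.

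**6. Reading B, group of 30.** Simulation, 20,000 trials: room-air mean 52, 60 or 68, between-patient SD 8, per-draw SD 3 or 5, 2 L used below 55.

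- No true change: the recorded mean change is about 0, because switches balance (for example, 3.2 patients each way).
- True fall of 5 in everyone: the recorded mean is −4.0 to −3.0 with a shift of 9, and −2.8 to −0.6 with a shift of 20. Switching then runs mostly one way.

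**The case against.** The other side has good points, and several stand.

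- **Weight.** Section 10(i) says that this is not an efficacy trial; the primary endpoints are tolerance and hours of use. No sample size or decision rule uses a blood gas. This stands and limits the severity.
- **Size.** A reader might infer a false PaO2 fall of 27 to 40 mmHg under Reading A. The documents do not support that: titration to a saturation just above 90% would stop well short. Because that level is a floor and not a ceiling, larger gaps than in the near-target calculation remain possible.
- **Visit 2.** A reader might infer that the whole blood-gas outcome is invalid. Under Reading A, Visit 2 against Visit 13 is governed by one rule. An overall day effect that includes Visit 1a would still carry the mismatch.
- **The 2 L option.** A reader might infer that it biases the mean by itself. It does so only if oxygenation truly changes.
- **Overview note 5.** It refers back to note 2 and might seem to put a later gas on titrated oxygen. The figure is not shown, so nothing can rest on it.
- **Recording.** The protocol text does not require oxygen at the draw to be recorded, but the case report forms are not in the documents and a field may exist.

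One could also argue that the footnote, being the more specific text, obviously governs. Nothing says so, and the baseline paragraph is equally specific about its own draw.

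**Conclusion.** The concern holds as an inconsistency in live instructions with a real consequence for secondary outcomes. Followed as written, the baseline and Day 90 texts compare an on-oxygen gas with a room-air gas. PaO2 then falls spuriously, and PaCO2 may fall in a way that resembles benefit. If the footnote governs throughout, the mean is sound when nothing changes but understates a true decline.

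The size cannot be derived from the documents. Under the assumptions shown, the bias in mean PaO2 runs from about 1 mmHg upward, and its sign depends on the reading. The text conflict and the missing oxygen term do not depend on those assumptions. The feasibility conclusions are unaffected. The change should be made because an unrecorded oxygen condition cannot be recovered after the draw.

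**What to change.** State one rule for Visits 1a, 2 and 13, and align all the blood-gas texts in Section 10(g), including overview notes 2 and 5:

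- Draw on room air after 20 minutes off the device and off any other oxygen.
- State the SpO2 threshold for switching to a fixed 2 L by standard cannula, and the time on 2 L before the draw. The protocol's working oxygen target is 90%; the investigator should confirm or replace it as the threshold.
- A patient who needs 2 L at Visit 1a is drawn on 2 L at later visits. A patient who first needs it later is drawn on 2 L for safety and reported as having worsened oxygenation.
- Record oxygen flow and SpO2 at each draw.
- Report the number and direction of condition changes. Show PaO2, PaCO2 and pH changes for all pairs, with oxygen condition as a term or flag, and for same-condition pairs as a sensitivity analysis. A worst-rank PaO2 analysis is optional.

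The cost is two recorded fields per draw and a small extra analysis. Neither analysis is clean alone, so both are needed. Under this rule chance switching runs one way: in the simulation 0.7 to 3.5 of 30 patients switch with no true change, which would lift an unadjusted all-pairs PaO2 mean by 0.7 × 9/30 = 0.2 to 3.5 × 20/30 = 2.3 mmHg for shifts of 9 to 20. Same-condition pairs (about 23 to 29 of 30) drop patients who fail room air later. For PaO2 they gave +0.1 to +1.2 with no change and −4.6 to −3.1 with a true fall of 5. Similar selection may affect PaCO2 and pH and should be stated.

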The primary endpoints of this study are the feasibility of oxygen therapy by HNHF-O2 at home over a 90-day period in terms of tolerance and hours of use. Descriptive statistics will be used to characterize the patient population in terms of demographic factors and severity of airflow obstruction. Changes in PaO₂, PaCO₂ and pH across the days will be done by analysis of variance. The effect of baseline PaCO₂ on change in PaCO₂ with HNHF-O2 therapy will be analyzed as an independent effect on change in PaCO₂ levels with HNHF-O2. Changes in respiratory rate, heart rate, blood pressure accessory muscle use will also be assessed by analysis of variance. Patient tolerance and side effects will also be measured across days of use per patient and across days in all patients as group trends. Hours of use per device log and per patient diary will be independently analyzed and compared to one another. The impact on change in exacerbation frequency and severity will be analyzed. Changes in spirometry, 6MWD, GOLD grade and class and BODE scores prior to and after 90 days of HNHF-O2 will be analyzed.

This is a pilot study in which the primary outcome is to determine the feasibility of using high-flow nasal oxygen in patients with COPD who have been recently discharged from the hospital with a COPD exacerbation. As such it is not an efficacy trial and is powered based on the ability to detect safety issues or unforeseen problems. The sample size has been estimated based on the method described by Viechtbauer, et.al.⁷

The safety issue we have identified is the need to withdraw therapy because HNHF-O2 is not tolerated by the subject.

The formula for this calculation is based on the probability of observing at least one of these events:

$$P(x > 0) = 1 - (1 - \pi)^n \text{ where}$$

x = the number of events that occur across the total number of participants
and

π = the probability that the event will occur.

Solving for n yields:

$$n = \frac{\ln(1 - \gamma)}{\ln(1 - \pi)}$$

Where γ = the confidence threshold.

Using a 95% confidence threshold and 15% probability that an event (need to discontinue due to intolerance) occurs the sample size required is:

Outpatient HNHF-O2 Protocol

Version 3.0

10/06/2017

$$n = \frac{\ln(1-0.95)}{\ln(1-0.1)} = 28.4 \text{ subjects.}$$

The number of subjects has been increased to 36 to accommodate screen failures and dropouts and to provide evaluable data on 30 subjects.

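### The baseline blood gas has two incompatible sampling conditions (titrated oxygen and room air) and Day 90 is on room air, so the change in PaO2 from Visit 1a may reflect inspired oxygen

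*Combined protocol and SAP*

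**What the plan says.** All the sampling instructions are in section 10(g) of the combined protocol and SAP.

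On oxygen:
- The baseline narrative takes an "arterial blood gas after 5 minutes of inspiring supplemental oxygen to keep" SaO2 above 90%. This text comes before the two-week diary run-in, so it concerns the visit headed "Visit 1a Baseline" in the schedule.
- Overview footnote 2 has "ABG 5 minutes after inspiring O₂ to maintain SaO₂ >90" percent. Overview footnote 5 refers back to footnote 2, but the figure it belongs to is not shown.

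On room air:
- The diamond footnote on the blood-gas row of the schedule, marked at Visits 1a, 2 and 13: "For ABGs, the test will be done on room air after the participant has been off the Airvo device for 20 minutes". It adds an exception: "If the participant starts to desaturate, then it can be done on 2L of oxygen".
- The Day 90 list: "Arterial blood gas on room air after the participant has been off the Airvo Device for 20 minutes".
- The arterial blood gas paragraph under Study procedures, which names no visit: "Blood gases will be obtained on room air after the patient has been off the Airvo device for 20 minutes".

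The analysis text, identical in sections 10(f) and 10(i), reads "Changes in PaO₂, PaCO₂ and pH across the days will be done by analysis of variance". It also plans to examine the effect of baseline PaCO2 on the change in PaCO2. It does not mention inspired oxygen.

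**The concern.** Visit 1a has two instructions that cannot both be followed, and no text ranks them. The room-air wording counts time since the device came off, yet the device is first placed at Visit 2. A coordinator could reasonably take it as a rule for later visits and use the oxygen instruction at baseline. Inspired oxygen would then differ between the first and last gas.

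PaO2 depends directly on inspired oxygen. The protocol describes an open-label study of thirty patients with no control arm, so nothing would cancel such a shift. The abstract names long-term gas exchange as an area where data are lacking, so these results are likely to be read with interest even though they are not primary. If staff resolve the conflict differently from patient to patient, the condition will also vary within the dataset. Unless oxygen flow was recorded at each draw, that could not be sorted out afterwards.

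**Working it through.** The plan gives no figure to reproduce here. The check sets the instructions side by side and then gauges the size of the problem.

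**1. Condition at each draw, by the text followed**

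| Text followed | Visit 1a | Visit 2 | Visit 13 (Day 90) |
|---|---|---|---|
| The two visit narratives, procedures text elsewhere | titrated oxygen | room air | room air |
| Diamond footnote throughout | room air (2 L if desaturating) | same | same |
| Overview footnotes 2 and 5, if footnote 5 marks the last visit | titrated oxygen | not stated | titrated oxygen |

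Only the first row puts a change of inspired oxygen between Visit 1a and Day 90. Even there, Visit 2 to Day 90 is nominally matched on room air. It is unclear, however, whether the Visit 2 draw comes before first device use. An analysis of variance over all three draws would still include the Visit 1a step. The third row cannot be confirmed without the figure, and it contradicts the Day 90 list.

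**2. Possible size for PaO2 in the first row, with nobody on 2 L at Day 90**

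All inputs are assumptions; the documents give none of them. They are PaCO2 50 mmHg at both visits, sea-level pressure (760 − 47 = 713 mmHg), respiratory quotient 0.8, FiO2 0.24 to 0.28 on oxygen, and an arterial/alveolar ratio of 0.55 to 0.65.

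Alveolar PO2 = FiO2 × 713 − PaCO2/0.8, and PaO2 = ratio × alveolar PO2.

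- Air: 0.21 × 713 − 62.5 = 87.2
- FiO2 0.24: 171.1 − 62.5 = 108.6
- FiO2 0.28: 199.6 − 62.5 = 137.1

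| Ratio | PaO2 on air (SaO2) | PaO2 at 0.24 (SaO2) | PaO2 at 0.28 (SaO2) | Fall from 0.24 to air | Fall from 0.28 to air |
|---|---|---|---|---|---|
| 0.55 | 48.0 (83.4%) | 59.7 (90.5%) | 75.4 (95.0%) | 11.8 | 27.5 |
| 0.65 | 56.7 (89.1%) | 70.6 (93.9%) | 89.1 (96.9%) | 13.9 | 32.4 |

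SaO2 = 1/(23400/(P³ + 150P) + 1). The ratios were chosen so that patients fall below 90% on air and exceed it on oxygen.

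With no true change, PaO2 would therefore be about 12 to 32 mmHg lower at Day 90. If only half the patients changed condition, the mean shift would be 0.5 × 11.8 = 5.9 to 0.5 × 32.4 = 16.2 mmHg. For comparison, the 95% confidence half-width for a mean change in 30 patients is t(0.975, 29) × SD/√30, which is 3.7 mmHg for an assumed SD of 10 and 5.6 mmHg for an SD of 15.

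**3. Effect of the 2 L exception at Day 90**

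Assume that 2 L gives an FiO2 of 0.28.

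- Patient titrated to 0.24 at baseline: PaO2 rises by 0.55 × (0.28 − 0.24) × 713 = 15.7 to 0.65 × 28.52 = 18.5 mmHg.
- Patient titrated to 0.28 at baseline: no shift.

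So even the sign depends on how the exception is used.

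**The case against.** The best defence is that the room-air rule appears three times, that its schedule footnote sits on the blood-gas row and so covers Visit 1a, and that the oxygen wording is a leftover. On that view the main condition is matched and the remedy is a wording correction. This may well be what the sponsor intends, but no text says so, and the exception still needs attention. It has no saturation trigger, is absent from the Day 90 list and the procedures paragraph, and applies to patients who are on oxygen as usual care.

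A second point stands in full. The Visit 2 gas offers a nominally matched comparison with Day 90 even if the narratives are followed, so not every planned blood-gas comparison is compromised.

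A third also stands. Patients who fall to 83 to 89% on air are plausibly the ones who would be given 2 L, so the 12 to 32 mmHg range is not a prediction.

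A reader might infer that the PaCO2 result, central in a hypercapnic population, is shown to be biased. It is not. A PaCO2 or pH shift is possible, but its size cannot be derived from the documents.

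A reader might also infer that feasibility is in doubt. The primary endpoints are tolerance and hours of use, the sample size rests on intolerance, and section 10(i) disclaims efficacy. None of these depends on a blood gas.

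**Conclusion.** The contradiction at Visit 1a is certain, because it is on the face of the current text. Its consequence is conditional. If the two visit narratives are followed, the Visit 1a to Day 90 change in PaO2 is confounded with inspired oxygen; the PaCO2 and pH changes and the baseline-PaCO2 analysis may be. If the schedule footnote is followed at every visit, only unequal use of the 2 L exception remains.

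The 12 to 32 mmHg figure shows that the problem could exceed the precision of a 30-patient mean. It rests wholly on assumed inputs and on no oxygen being given at the Day 90 draw. With 2 L in use, the shift could be smaller, zero or in the other direction. The documents therefore do not support the tempting conclusion that the blood-gas results must be biased downward. Nor would uniform sampling alone allow a change in a single arm to be credited to the device. The point is worth correcting and leaves the primary endpoints and the sample size untouched.

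**What to change.** 1. Delete the on-oxygen wording from the baseline narrative and from overview footnote 2, so that the room-air rule in the schedule footnote governs Visits 1a, 2 and 13.
2. Give an SpO2 threshold for the 2 L exception, and repeat the exception in the Day 90 list and the procedures paragraph.
3. Record oxygen flow at every draw, and whether the Visit 2 draw precedes device use.
4. Report blood-gas change overall and by sampling condition, with condition-matched pairs as a sensitivity analysis.

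A fixed oxygen flow for each patient at all visits would be a workable alternative where room air is judged unsafe. What matters is one rule, applied and recorded.

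The cost is protocol wording, a recorded oxygen flow and draw timing, and one extra table, with no additional arterial punctures. The downside is that patients come off oxygen briefly at baseline. The 2 L safeguard must therefore stay, and some pairs will still be taken under mixed conditions.
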